8.4 ADVERSE EVENTS AND SERIOUS ADVERSE EVENTS

8.4.1 Definition of Adverse Event

Adverse event means any untoward medical occurrence associated with the use of an intervention in humans, whether or not considered intervention-related (21 CFR 312.32 (a)).

8.4.2 Definition of Serious Adverse Events (SAE)

An adverse event (AE) or suspected adverse reaction is considered "serious" if, in the view of either the investigator or sponsor, it results in any of the following outcomes: death, a life-threatening adverse event, inpatient hospitalization or prolongation of existing hospitalization, a persistent or significant incapacity or substantial disruption of the ability to conduct normal life functions, or a congenital anomaly/birth defect. Important medical events that may not result in death, be life-threatening, or require hospitalization may be considered serious when, based upon appropriate medical judgment, they may jeopardize the participant and may require medical or surgical intervention to prevent one of the outcomes listed in this definition. Examples of such medical events include allergic bronchospasm requiring intensive treatment in an emergency room or at home, blood dyscrasias or convulsions that do not result in inpatient hospitalization, or the development of drug dependency or drug abuse.

8.4.3 Classification of an Adverse Event

8.4.3.1 Severity of Event

For adverse events (AEs) not included in the protocol defined grading system, the following guidelines will be used to describe severity.

- **Mild** – Events require minimal or no treatment and do not interfere with the participant's daily activities.
- **Moderate** – Events result in a low level of inconvenience or concern with the therapeutic measures. Moderate events may cause some interference with functioning.
- **Severe** – Events interrupt a participant's usual daily activity and may require systemic drug therapy or other treatment. Severe events are usually potentially life-threatening or incapacitating. Of note, the term "severe" does not necessarily equate to "serious".

8.4.3.2 Relationship to Study Intervention

All adverse events (AEs) must have their relationship to study intervention assessed by the investigator who examines and evaluates the participant based on temporal relationship and his/her clinical judgment. The degree of certainty about causality will be graded using the categories below. In a clinical trial, the study product must always be suspect.

- **Related** – The AE is known to occur with the study intervention, there is a reasonable possibility that the study intervention caused the AE, or there is a temporal relationship between the study intervention and event. Reasonable possibility means that there is evidence to suggest a causal relationship between the study intervention and the AE.
- **Not Related** – There is not a reasonable possibility that the administration of the study intervention caused the event, there is no temporal relationship between the study intervention and event onset, or an alternate etiology has been established.

OR

- **Definitely Related** – There is clear evidence to suggest a causal relationship, and other possible contributing factors can be ruled out. The clinical event, including an abnormal laboratory test result, occurs in a plausible time relationship to study intervention administration and cannot be explained by concurrent disease or other drugs or chemicals. The response to withdrawal of the study intervention (dechallenge) should be clinically plausible. The event must be pharmacologically or phenomenologically definitive, with use of a satisfactory rechallenge procedure if necessary.
- **Probably Related** – There is evidence to suggest a causal relationship, and the influence of other factors is unlikely. The clinical event, including an abnormal laboratory test result, occurs within a reasonable time after administration of the study intervention, is unlikely to be attributed to concurrent disease or other drugs or chemicals, and follows a clinically reasonable response on withdrawal (dechallenge). Rechallenge information is not required to fulfill this definition.
- **Potentially Related** – There is some evidence to suggest a causal relationship (e.g., the event occurred within a reasonable time after administration of the trial medication). However, other factors may have contributed to the event (e.g., the participant's clinical condition, other concomitant events). Although an AE may rate only as "possibly related" soon after discovery, it can be flagged as requiring more information and later be upgraded to "probably related" or "definitely related", as appropriate.
- **Unlikely to be related** – A clinical event, including an abnormal laboratory test result, whose temporal relationship to study intervention administration makes a causal relationship improbable (e.g., the event did not occur within a reasonable time after administration of the study intervention) and in which other drugs or chemicals or underlying disease provides plausible explanations (e.g., the participant's clinical condition, other concomitant treatments).
- **Not Related** – The AE is completely independent of study intervention administration, and/or evidence exists that the event is definitely related to another etiology. There must be an alternative, definitive etiology documented by the clinician.

8.4.3.3 Expectedness

The Principal Investigator or designated study team member will be responsible for determining whether an adverse event (AE) is expected or unexpected. An AE will be considered unexpected if the nature, severity, or frequency of the event is not consistent with the risk information previously described for the study intervention.

Abbreviated Title: Pediatric Optic-to-Audio Device Study

Version Date: March 8, 2022

8.4.4 Time Period and Frequency for Event Assessment and Follow-Up

The occurrence of an adverse event (AE) or serious adverse event (SAE) may come to the attention of study personnel during study visits and interviews of a study participant presenting for medical care, or upon review by a study monitor.

All AEs including local and systemic reactions not meeting the criteria for SAEs will be captured on the appropriate case report form (CRF). Information to be collected includes event description, time of onset, clinician's assessment of severity, relationship to study product (assessed only by those with the training and authority to make a diagnosis), and time of resolution/stabilization of the event. All AEs occurring while on study must be documented appropriately regardless of relationship. All AEs will be followed to adequate resolution.

Any medical condition that is present at the time that the participant is screened will be considered as baseline and not reported as an AE. As CLN3 is a neurodegenerative, multisystemic disease, progression or new onset of symptoms may be part of the disease process and unrelated to the intervention. Problems listed in **Table 2** will not be reported to the IRB as adverse events unless increase in frequency is noted.

Changes in the severity of an AE will be documented to allow an assessment of the duration of the event at each level of severity to be performed. AEs characterized as intermittent require documentation of onset and duration of each episode.

A designated study team member will record all reportable events with start dates occurring any time after informed consent is obtained until 7 (for non-serious AEs) or 30 days (for SAEs) after the last day of study participation. At each study visit, the investigator will inquire about the occurrence of AE/SAEs since the last visit. Events will be followed for outcome information until resolution or stabilization.

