2.3 RISK/BENEFIT ASSESSMENT

2.3.1 Known Potential Risks

Efforts will be made to reduce physical and psychological stress associated with study participation. These procedures will be explained to the individual participants and to their parents/guardians.

- A. OrCam MyEye 2 Device and Use.** Non-significant risks are associated with the use of the device when following the manufacturer's User Guide (**Appendix J**). The device is worn as an accessory to regular eyeglass frames. The relative proportion of the device to a pediatric participant is shown in **Appendix K**. If an individual does not have glasses, they may experience discomfort with wearing glasses for the first time. The increase in auditory inputs may be irritating. The device use acclimation process may be frustrating. These are expected to improve with repeated use.
- B. Medical Evaluations.** Minimal risks are associated with the physical, the Unified Batten Disease Rating Scale (UBDRS), and neuropsychologic examinations. Multiple independent evaluations may be stressful to a child or an impaired participant.
- C. Ophthalmologic Evaluation.**
 A standard ophthalmologic exam includes dilation. Iris dilation can make participants transiently sensitive to light.
- D. Audiologic Evaluation.** For the hearing test the participant will wear headphones or soft foam earplugs. They will then be exposed to tones and words which vary in loudness and asked to respond to the sounds. This testing involves minimal discomfort.
 Acoustic reflex measurement allows the audiologist to further examine the integrity of the acoustic reflex arc which relies on functional integrity of the middle ear system, inner ear, seventh and eighth cranial nerves and auditory pathways in the lower brainstem. For this test, very brief, somewhat loud tones are presented to each ear. In a normal-hearing ear, the stapedius muscle in the middle ear contracts in response to loud sounds presented

at levels of about 70-100 dB HL (decibels hearing level). In this test, the audiologist presents tones at these levels and determines whether there is an acoustic reflex and what level of sound is required to produce the reflex. This is a standard audiology test.

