8.4.5 Adverse Event Reporting

The Principal Investigator and designated study team members are responsible for detecting, documenting, and reporting unanticipated problems, adverse events (AEs), including serious adverse events (SAEs), and deviations in accordance with NIH policy, and IRB requirements. Relatedness to the research of all serious adverse events will be determined by the PI in consultation with the CD.

Serious unanticipated problems and serious protocol deviations will be reported to the IRB and CD as soon as possible and in writing not more than 7 days after the PI first learns of the event.

Deaths will be reported to the Clinical Director within 7 days after the PI first learns of the event.

All adverse events, deviations, and unanticipated problems will be summarized and reported at the time of Continuing Review.

Table 2. Adverse events associated with CLN3

Category		Adverse Event
HEENT	Eyes	Low vision/blindness; abnormal movements (nystagmus); photophobia; visual hallucination
	Ears	Auditory hallucination; abnormalities in Behavioral Hearing and ABR tests
	Oromotor/ Speech	Dysphagia; drooling; dysarthria

Cardiovascular		Sinus arrhythmias; prolonged ECG intervals; elevated BNP
Hematology		Decreased serum iron, % saturation
Endocrinology		Abnormal TSH; low vitamin D
Musculoskeletal		Abnormal gait; falls; scoliosis; in-toeing; abnormal muscle tone; tremors
Neurological		Brain atrophy; seizures; cognitive impairment; memory impairment; sleep disruption; fatigue
Psychiatric/Behavioral		Irritability; aggression; perseveration; anxiety; mood instability

ABR: auditory brainstem response. BNP: pro-brain natriuretic peptide. ECG: electrocardiogram. HEENT: head, eyes, ears, nose, throat. TSH: thyroid stimulating hormone

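### A condition present at screening is not reported as an adverse event even if it worsens on the device, and the CLN3 exception to IRB reporting is lifted only by a rise in frequency

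*Combined protocol and SAP*

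**What the plan says.** Section 8.4.4 contains two separate rules.

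- **Baseline rule:** any medical condition "present at the time that the participant is screened will be considered as baseline and not reported as an AE". It applies to every participant and has no exception.
- **IRB rule:** problems in the table of CLN3-associated events (section 8.4.5) "will not be reported to the IRB as adverse events unless increase in frequency is noted". The table includes seizures, falls, auditory hallucination and, under psychiatric and behavioural problems, "Irritability; aggression; perseveration; anxiety; mood instability".

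The same section sets a broad duty to document: "All AEs occurring while on study must be documented appropriately regardless of relationship". It also tracks severity: "Changes in the severity of an AE will be documented to allow an assessment of the duration of the event at each level of severity". On recording, it says: "A designated study team member will record all reportable events with start dates occurring any time after informed consent is obtained".

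Section 2.3.1, on device risks, says: "The increase in auditory inputs may be irritating". Section 3 makes adverse events the primary safety endpoint, and section 9.4.2 analyses them by descriptive statistics alone.

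**The concern.** The safety conclusion depends on what is counted as an adverse event. The study is open-label, has no concurrent untreated group and has no data and safety monitoring committee (sections 4.1, 4.2 and 10.5), so no comparison would reveal events lost through the definition.

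Section 2.2 describes behavioural, psychiatric, seizure and motor disorders as common in CLN3. Many CLN3 participants may therefore bring such a condition to screening. For them, the plausible harm from an audio device is aggravation of an existing problem, and the baseline rule does not count aggravation. A safety summary compiled as the rule is written could look cleaner than what happened.

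**Working it through.** The plan states no figure on this point, so the check is mainly a comparison of passages.

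**Step 1. Does another sentence bring a worsened baseline condition back in?**

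| Place | What it covers | Restores worsening? |
|---|---|---|
| 8.4.4, documentation and severity sentences | Events already classed as AEs | No; the baseline rule acts before them |
| 8.4.4, recording sentence | Reportable events, a term the section does not define | Unclear |
| 8.4.1, definition | Any untoward medical occurrence, related or not | Arguably, but the baseline rule is the more specific text |
| 7.1 | Changes from baseline prompt a review of management; findings that are new and clinically relevant are reported as AEs | In part; whether aggravation of an old condition is new is left open |
| 8.3, item 6 | Scheduled contacts ask about events relating to device use | Gathers information but does not reclassify a baseline condition; also narrower than the any-relationship duty in 8.4.4 |

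None of these says that worsening of a baseline condition is an adverse event. Two staff members could classify the same worsening differently, and the most specific sentence favours leaving it out.

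**Step 2. What does the IRB rule limit?** Its wording concerns reporting to the IRB, and the only trigger that lifts it is frequency. Against the rest of the plan:

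- Expectedness (8.4.3.3) and unanticipated problems (8.5.1) both turn on the kind, severity or frequency of an event. The latter also requires at least a possible relation to the research.
- Section 8.4.5 has all adverse events summarised at Continuing Review, with no exception for the listed problems.
- Section 8.4.2 gives convulsions without hospital admission as an example of an event that may be serious, and 8.4.6 requires serious events to be reported within 7 calendar days. Seizures are in the table, and nothing says which rule prevails.
- The rule cites Table 2, but section 8.1.2 also has a Table 2, on eligibility evaluations. The rule is not expressly confined to CLN3 participants.

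**Step 3. Overlap with device effects.** Irritating auditory input (2.3.1) overlaps with irritability in the table. This is an inference, since a child annoyed by the sound need not have the behavioural symptom. Section 5.2 excludes auditory hallucinations only if they occur daily, so a child with less frequent ones could enrol, and under 8.4.4 they would be baseline.

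**Step 4. Scale, for illustration only.** The documents do not say how many participants have a given problem at screening. Suppose *k* of the 20 CLN3 participants have it, no non-CLN3 participant has it, and its worsening is never counted. A summary with no events then rests on *n* = 30 − *k* children. The exact one-sided 95% upper bound on the event rate is 1 − 0.05^(1/*n*):

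- *k* = 0, *n* = 30: 1 − 0.05^(1/30) = 9.5%
- *k* = 10, *n* = 20: 1 − 0.05^(1/20) = 13.9%
- *k* = 20, *n* = 10: 1 − 0.05^(1/10) = 25.9%

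Section 9.3.1 makes all participants evaluable from first use of the device, so the stated denominator would remain 30. The last line is a worst case. The CLN3 share of the sample is 20/30 = 67%.

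**The case against.** The strongest reply is that capture is broad. All adverse events go on the case report form whatever their cause, and the general definition would take in a new seizure or fall. Sections 7.1 and 8.5.1 give changes from baseline, severity and relatedness some route. The IRB rule's own reference to rising frequency also suggests that the authors thought worsening of an existing problem could be an adverse event.

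Much of this stands. A reader might infer that the listed CLN3 problems drop out of the safety endpoint altogether. The documents do not support that: the exception is to IRB reporting, the endpoint is a summary of adverse events rather than of IRB reports, and new-onset irritability, falls or seizures should appear in it. Nor do all the stated device risks fall in the table; frustration and discomfort from glasses are absent. It also cannot be said that baseline frequency goes unrecorded. Medical history is scheduled at screening, and the Unified Batten Disease Rating Scale is done for CLN3 participants not co-enrolled in 18-CH-0002, but the forms are not shown. IRB reporting also follows NIH policies that are not reproduced.

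What the reply does not reach is the baseline rule. The documentation and severity sentences presuppose an adverse event, and section 7.1 ties AE reporting to new findings. That the IRB rule seems to assume worsening can count, while the baseline rule says otherwise, is a reason to reconcile them.

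**Conclusion.** The concern holds in two parts. First, followed as written, the baseline rule can remove worsened or device-aggravated pre-existing conditions from a primary endpoint, and section 7.1 is only a partial safeguard. Second, the frequency-only trigger for IRB reporting is inconsistent with sections 8.4.2, 8.4.3.3, 8.4.5, 8.4.6 and 8.5.1. The second part concerns oversight and leaves capture of new-onset events untouched.

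The size is unknown. Only a participant whose screening condition worsens is affected, so 20 for CLN3 problems and 30 for any screening condition are ceilings, not estimates. The conclusion assumes that staff apply section 8.4.4 literally and that no unseen form or policy supplies the missing clause. The change is worth making: it corrects a stated rule on a primary endpoint at little cost.

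**What to change.** 1. Add to the baseline sentence: *unless it worsens in severity or frequency from screening, or is suspected to be related to the device, in which case it is recorded as an AE*.
2. State that the exception for listed CLN3 problems affects IRB reporting only, does not override reporting of serious adverse events or unanticipated problems, and does not apply when severity increases or a device relation is suspected. Check this against the applicable NIH reporting policies.
3. Reconcile section 8.4.4 with sections 7.1 (changes from baseline), 8.3 item 6 (scope of the scheduled contacts) and 8.4.5 (Continuing Review), and define reportable events.
4. Record baseline frequency and severity of the listed problems in the medical history already scheduled at screening, so that an increase has a reference.
5. Renumber the CLN3 table, correct the citation, and say whether the exception applies only to CLN3 participants.

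The cost is a few clauses, one addition to the screening form and a few more adverse-event records. No visit or procedure is added.

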1.3 SCHEDULE OF ACTIVITIES (SOA)

Procedures	Screening ^{a,d} Up to Day -1	Enrollment Baseline Day 1	Day 2 ^b	Day 3 to 4 ^b	1-Week Evaluations Day 5 ^b	Day 6-11 ^b	Day 12 ^b	Day 13-18 ^b	Day 19 ^b	Day 20-25 ^b	Day 26 ^b	Day 27-32 ^b	1-Month Evaluations Day 33 ^{b,c}
Informed consent ^c	X												
Demographics ^c	X												
Medical history ^c	X												
Physical exam ^d	X												
Vital signs ^d	X												
Ophthalmic evaluation ^d	X												
Neuropsychologic evaluation ^c	X												X ^{d or h}
Audiologic evaluation ^d	X												
UBDRS ^{c,e}	X												
Device training ^{c,f}		X ^d	X ^d	X ^{d or h}	X ^d	X ^h	X ^h	X ^h	X ^h				
Device use ^g			X ^{d or h}	X ^{d or h}		X ^h	X ^h	X ^h	X ^h	X ^h	X ^h		
Adverse events review ^c					X ^{d or h}		X ^h		X ^h		X ^h		X ^{d or h}
Feasibility test ^{c,i}		X ^d			X ^d								X ^{d or h}
Feasibility questionnaire ^{c,j}					X ^{d or h}								X ^{d or h}
Function test ^k		X ^{l, d}			X ^{l, d}								X ^{m, d or h}
Ability questionnaire ⁿ		X ^d			X ^{d or h}								X ^{d or h}
Applicability questionnaire ^o		X ^d											
Quality of Life questionnaires ^p		X ^d											X ^{d or h}
Phlebotomy ^d	X												
Research biospecimen collection ^q	X												

^a Screening evaluations can be done under 18-CH-0002 protocol if participant consented to co-enroll, or under this protocol. Previous evaluations/procedures within stated time frames (**Section 8.1.2**) will be accepted in lieu of repeating.

Abbreviated Title: Pediatric Optic-to-Audio Device Study

Version Date: March 8, 2022

^b +/- 2 days, except for Day 2 to 4 range may be +2 days

^c By in-person or remote technology methods

^d At NIH CC

^e Only in participants with CLN3-related conditions who are not co-enrolled in study 18-CH-0002.

^f **Appendix J** - OrCam MyEye 2 User Guide, Software Version 8.2-EN, Jan 2020.

^g By participant for minimum of 15-30 minutes per day. If participant/parents/guardians encounter issues with device use, they may contact the study team and a video- or audioconference will be scheduled as appropriate.

^h At home

ⁱ **Appendix A.** To be administered by study team to participant

^j **Appendix B.** To be administered by study team to participant if able, and parents/guardians

^k **Appendix C.** To be administered by study team to participants.

^l Full Function Test done with evaluator and participant at NIH CC or partial Function Test done via remote technology (e.g., videoconferencing).

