The audiology evaluation will include measurement of auditory evoked potentials. For this test, the participants will wear either headphones or soft, foam earplugs. Electrodes will be taped to the participants' head and the electrical response to sound will be recorded. This testing involves minimal discomfort and risk.

- E. Neuropsychologic Evaluations.** Participants may fatigue or get frustrated from answering many questions. Breaks will be provided to minimize these potential issues.
- F. Phlebotomy.** An anesthetic cream such as EMLA may be used to decrease discomfort. Infection and bruising are possible at the site of the blood draw.
- G. Cheek swab/Saliva collection.** The collection may be inconvenient. The cheek swab may cause temporary oozing of blood that should be minimal.
- H. Urine collection.** This collection may be inconvenient.
- I. Skin biopsy.** The biopsy may hurt. This can be minimized by administration of local anesthetics. The site may leave a faint scar. Individuals with history of excessive keloid formation will not have a skin biopsy done. Bleeding and infection are minimal risks.
- J. Genetic Testing.** Genetic information obtained from participation in research could be misused for discriminatory purposes. However, state and federal laws provide some protections against genetic discrimination. Researchers who will have access to genetic information about the participants will take measures to maintain the confidentiality of this information. Individuals enrolled in this protocol would already have the diagnosis of CLN3-related conditions or a genetic cause of low vision, with its attendant risks of insurance and employment discrimination. If the underlying genetic cause for the low vision is not known and it is applicable to identify, then the participant will be referred to protocol "Evaluation of Patients with Genetic Disorders" (16-CH-0103). To the fullest extent possible, the investigators will not disclose to third parties any information about the participants without their expressed consent.
- K. Sample confidentiality.** Specimens not being used for clinical care or standard clinical tests which are sent to various laboratories will have identifiers removed and be coded. This code and clinical data will be maintained on password protected computers and in locked offices.

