4.2 SCIENTIFIC RATIONALE FOR STUDY DESIGN

Currently, there is no device similar to the OrCam available or in accepted use for individuals with CLN3. In addition, there is also no data available on the use of this device in children with low vision. Thus, a combined cohort of pediatric participants with and without CLN3-related disorders will optimize recruitment potential, and provide preliminary information for evaluation of feasibility and efficacy in pediatrics, and specifically in individuals with CLN3-related conditions. To assess efficacy, we will use the study participants' baseline data as controls. This option encompasses the least number of confounding factors for a cohort of small size.

In the CLN3 natural history study (18-CH-0002), accrual rate averages at 8-10 per year. Not all of these individuals will meet the eligibility criteria for this proposed study. However, we anticipate, based on experience with interventional trials of other rare diseases, that families hesitant to participate in an observational study would be more open to participating in an interventional study. Given these considerations, we anticipate an accrual rate of 5 participants per year and a reasonable potential to enroll 20 CLN3 participants over 2-3 years. We have also discussed potential eligible participants with local Ophthalmology groups (Howard University, Johns Hopkins, NEI), and the anticipated number for pediatric individuals with low vision and not CLN3-related condition is estimated to be in the same range. We plan to screen up to 50 participants.

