5.6 SCREEN FAILURES

Screen failures are defined as participants who consent to participate in the clinical trial but are not subsequently assigned to the study intervention or entered in the study. A minimal set of screen failure information is required to ensure transparent reporting of screen failure participants, to meet the Consolidated Standards of Reporting Trials (CONSORT) publishing requirements, and to respond to queries from regulatory authorities. Minimal information includes demography, screen failure details, eligibility criteria, and any serious adverse event (SAE).

Individuals who do not meet the criteria for participation in this trial (screen failure) because of a temporary or reversible deficit in hearing ability may be rescreened. Rescreened participants should be assigned the same participant number as for the initial screening.

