6 STUDY INTERVENTION

6.1 STUDY INTERVENTIONS(S) ADMINISTRATION

6.1.1 Study Intervention Description

OrCam MyEye 2 is an FDA class 1 device (<https://www.accessdata.fda.gov/scripts/cdrh/cfdocs/cfRL/rl.cfm?lid=397540&lpcd=HPG>). The main components include a 13 megapixels camera, a 3.7V DC (nominal 320mAH) battery, and ancillary charging and glass-mounting supplies. The OrCam MyEye 2 is available in only one size that has dimensions of 76x21x14.9 mm, and weighs 22.5 g. Additional visual and descriptions of the device, its set-up and functions are provided in **Appendices I-K**. The use of the OrCam in this study will be according to the manufacturer's specifications. The device is not intended as an implant and does not present potential for serious risk to the health, safety, or welfare of a subject. Due to its risk profile, the device should be considered a non-significant risk device.

Participants will be trained and asked to use the device for at least 30 minutes daily as indicated in the **Schedules of Activities**. All participants meeting eligibility criteria will enroll in the 1-week study and be exposed to the device use for 5 days. Participants may enter the additional 1-month study if parents/guardians/participants endorse desire to continue using the device at home.

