7.2 PARTICIPANT DISCONTINUATION/WITHDRAWAL FROM THE STUDY

Prior to removal from study, effort will be made to have all participants complete a safety evaluation approximately 1 week following the last use of study device.

Participants are free to withdraw from participation in the study at any time upon request.

An investigator may discontinue or withdraw a participant from the study for the following reasons:

- Significant study intervention non-compliance
- If the participant meets an exclusion criterion (either newly developed or not previously recognized) that precludes further study participation
- Participant has completed the study follow-up period
- Death
- Screen Failure

The reason for participant discontinuation or withdrawal from the study will be recorded on the Discontinuation/Withdrawal Case Report Form (CRF). Participants who sign the informed consent form but do not receive the study intervention, i.e. the activities on enrollment/baseline

Abbreviated Title: Pediatric Optic-to-Audio Device Study

Version Date: March 8, 2022

day, may be replaced. Participants who sign the informed consent form, receive the study intervention, and subsequently withdraw, or are withdrawn or discontinued from the study, will not be replaced.

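### No scheduled contact falls inside the 7-day AE and 30-day SAE windows after last participation; the one partial safeguard is outside the Schedule and cannot reach screen failures

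*Combined protocol and SAP*

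**What the plan says.** Section 8.4.4 starts recording at informed consent and continues "until 7 (for non-serious AEs) or 30 days (for SAEs) after the last day of study participation". While a child is on study, every event is to be documented, whether or not it is related to the device. The active step it names is this: "At each study visit, the investigator will inquire about the occurrence of AE/SAEs since the last visit".

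The Schedule of Activities (Section 1.3) has a row "Adverse events review ^c", marked on Days 5, 12, 19, 26 and 33. Its footnote allows remote contact. No column follows Day 33.

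The second part of the study is optional. Section 6.1.1 says "Participants may enter the additional 1-month study if parents/guardians/participants endorse desire to continue using the device at home", and Section 6.4 ties the weekly adverse event contacts to that part.

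Section 7.2 says that, before removal from the study, effort will be made to have all participants "complete a safety evaluation approximately 1 week following the last use of study device". The Schedule has no matching row.

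Phlebotomy and research biospecimens, which can include a skin biopsy, are marked at Screening only. Section 2.3.1 says of the biopsy "Bleeding and infection are minimal risks", and also names infection and bruising for the blood draw. For screen failures, Section 5.6 states: "Minimal information includes demography, screen failure details, eligibility criteria, and any serious adverse event (SAE". On numbers, Section 4.2 says "We plan to screen up to 50 participants", and Section 5.7 gives an accrual goal of 30.

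Section 8.3, item 6, confines the adverse event review to events relating to use of the device. Section 9.3.1 makes participants evaluable for adverse events from first device use.

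**The concern.** Safety is half of the primary objective (Section 3) and is reported descriptively (Section 9.4.2), so the result is only as good as the asking. The protocol states a recording window but schedules nobody to fill it. A low count from such a period cannot be told apart from a period with no events. Three groups are affected: completers, children who stop at Day 5, and screen failures. The second group may include children who tolerated the device poorly. The third may have had an invasive research procedure, with infection as a named risk, and will never use the device.

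There is also a practical issue. Staff who follow the Schedule will not carry out Section 8.4.4, and staff who follow Section 8.4.4 must improvise, so late capture will vary from child to child.

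**Working it through.** No power or alpha figure is at issue; the check is day arithmetic and a comparison of sections. The protocol does not define the last day of participation. I take it as the last Schedule day attended.

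**1. Where the windows end.** Formula: last day + 7 for non-serious events, last day + 30 for SAEs.

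| Child | Last day | AE window ends | SAE window ends | Scheduled contacts in the window |
|---|---|---|---|---|
| Stops at Day 5 | 5 | 5 + 7 = Day 12 | 5 + 30 = Day 35 | 0 |
| Completes | 33 | 33 + 7 = Day 40 | 33 + 30 = Day 63 | 0 |
| Screen failure | last screening day, S | S + 7 | S + 30 | 0 |

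The Day 12, 19, 26 and 33 contacts fall within the SAE window of a Day 5 stopper by date. They do not count for that child, because Section 6.4 places the weekly contacts in the 1-month part and Day 33 is the 1-month evaluation.

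**2. What the Section 7.2 evaluation adds.** Formula: last device use + 7.

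- Day 5 stopper, last use Day 4: 4 + 7 = Day 11. This covers most of the window to Day 12, but not the SAE window to Day 35.
- Completer, last use Day 26 (the last marked device-use day): 26 + 7 = Day 33. This coincides with the existing visit and adds nothing after participation ends.
- Completer who uses the device to Day 32: 32 + 7 = Day 39, against windows ending on Days 40 and 63.
- Screen failure: there is no last use, so the clock has no start. Section 7.2 lists screen failure among its reasons for withdrawal, but the evaluation cannot be timed for such a child.

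In no case does it reach the end of a 30-day window, and no other section schedules an SAE query there.

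**3. How many screen failures.** Ceiling if both planned numbers are reached: 50 − 30 = 20. The number who were sampled and then failed could be anywhere from 0 to 20. It falls with fewer screened, with children who fail before sampling, and with samples already taken under 18-CH-0002. That last exemption does not extend to blood-related samples (Section 8.3, item 8).

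**4. Enrolled children and screening procedures.** Screening precedes Day 1. The Section 8.4.4 inquiry at each study visit therefore applies at Day 1 and Day 5 and covers a biopsy or blood draw done at Screening. Two provisions pull the other way. The scheduled review is device-only (Section 8.3, item 6), and the safety population starts at first use (Section 9.3.1). An event between consent and first use must be recorded under Section 8.4.4, yet it lies outside both.

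**5. Caveat.** The Schedule was read from extracted text. Column positions, notably the blank device-use cell for Days 27–32, should be checked against the original, since step 2 depends on them.

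**The case against.** The best defence is that the protocol does more than the Schedule shows. Section 7.2 is initiated by the team and worded for all participants. Section 7.1 collects adverse events when the intervention is discontinued. Section 6.4 has staff cross-check the diary daily in the first week. Section 8.4.4 asks at every visit. Section 5.6 sets a minimum record and does not tell staff to discard non-serious events. The device is described as non-significant risk.

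Much of this stands, and it rules out some stronger readings. A reader might infer that late events would surface only if families call in; Section 7.2 contradicts that. A reader might infer that biopsy infection is asked about in nobody; for enrolled children the visit inquiry contradicts that. A reader might also infer that Day 5 stoppers are reviewed less intensively, with one review against five. One review in one week and five over about five weeks are much the same rate.

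The defence does not supply a contact inside the windows. Sections 7.1, 6.4 and the visit inquiry all operate while the child is still attending or at the moment of stopping. Section 7.2 alone looks beyond that, with the limits shown above.

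**Conclusion.** The concern holds in this limited form. The Schedule has zero contacts inside the 7-day and 30-day windows for completers, Day 5 stoppers and screen failures. The Section 7.2 evaluation partly covers the 7-day window for device users if it is done. No SAE query is planned at 30 days for anyone. Screen failures who were sampled have no later inquiry at all.

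The conclusion rests on the extracted column positions and on taking the last attended Schedule day as the end of participation. The count of 20 is a ceiling. A reader might turn it into 40% of screened children left unfollowed (20/50), but the documents do not say how many will fail or how many will be sampled first. Nor do they support a conclusion that the biopsy is mistimed: no section orders it before the eligibility decision, and Section 8.1.1 allows genetic sequencing as part of screening, so some samples may serve eligibility. Screen-failure events also fall outside the safety population in Section 9.3.1, so for that group the issue is complete recording under Section 8.4.4, not bias in the primary safety summary.

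This should be corrected, but it does not undermine the design.

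**What to change.** - Enter the Section 7.2 evaluation in the Schedule as a brief remote adverse event contact about 7 days after last participation, and define that last day so that Sections 7.2 and 8.4.4 use the same clock.
- Add a remote SAE query at 30 days.
- Apply both to completers, to children who stop at Day 5, and to any screen failure who had a blood draw or biopsy.
- State in Section 5.6 that non-serious procedure events in screen failures are also kept.
- Reconcile the device-only scope in Section 8.3, item 6, and the first-use start in Section 9.3.1 with the from-consent, all-events rule in Section 8.4.4. If the safety population is to start at first use, say where earlier events are reported.
- Check the Schedule's columns against the original while editing it.

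The cost is a Schedule amendment and one or two short remote contacts per child by the existing team. Remote adverse event review is already permitted by the Schedule's footnote.
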